Within the 2 clinical populations (MCI/Prodromal and mild AD), subjects will be stratified at randomization by *ApoE4* status (positive or negative) and prior treatment with AChEIs or memantine or both (yes or no).

Sample Size Rationale***Sample Size Rationale in the MCI/Prodromal cohort***

Primary endpoint – derived ADCOMS: The sample size and design characteristics to test the hypothesis for the primary objective based on the primary endpoint were determined by means of simulations. Extensive study simulations have shown that a total of 500 subjects will be sufficient to demonstrate that the most likely ED₉₀ dose achieves a 25% improvement over placebo with a probability of at least 80% in the interim and final analyses. There is at least a 90% probability of study success for the dose response scenarios where treatment was considered to have a clinically meaningful treatment effect. Simulations have also shown that if there is no obvious dose effect, the probability of falsely claiming superiority to placebo is at most 5%.

For each of the 4 treatment groups (3 active doses and placebo), the final number of subjects per group will differ depending on the observed interim treatment responses.

vMRI: The null hypothesis is that there is no difference between active dose and placebo. There are 3 null hypotheses corresponding to 3 active doses. The alternative hypothesis is that at least 1 null hypothesis is false (1-sided). The null hypotheses will be tested using Dunnett's method with 1-sided alpha of 0.05. The statistical power was estimated through simulation for a moderate dose-response assumption that the percent reduction in change from baseline of total hippocampal volume compared with placebo would be 15%, 20%, and 25% corresponding to the 3 doses, respectively. The estimated power for actual planned study sample size is 78% at 18 months assuming an attrition rate of 20% at 18 months. Under a stronger dose-response assumption (ie, the percent reduction in change from baseline of total hippocampal volume compared with placebo is twice as much as that in the moderate dose-response assumption), the estimated power is at least 99% at 18 months.

Amyloid PET: The null and alternative hypotheses and statistical test are the same as those for vMRI. To estimate the sample size for the amyloid PET imaging subgroup at 18 months, a common SD of change from baseline was estimated at 0.33 and a reasonable mean difference between treatment and placebo was estimated as 0.25 (standardized uptake value ratio [SUVR]). Assuming a moderate dose-response, the best dose would achieve a difference of 0.25 (SUVR) and the middle and low doses would achieve a difference of 0.2

and 0.15 (SUVR), respectively, it would require a total of 100 subjects from all 4 arms at 18 months to achieve 80% power.

Sample Size Rationale for the Mild AD Cohort

ADCOMS at Month 18: The null hypothesis is that there is no difference between active dose and placebo. There are 2 null hypotheses corresponding to 2 active doses. The alternative hypothesis is that at least 1 null hypothesis is false. The null hypotheses will be tested using Dunnett's test with 2-sided alpha of 0.05 as described for the mild AD cohort in the secondary analysis section. The statistical power was estimated through simulation for the dose-response assumption that the percent reduction in change from baseline of ADCOMS at 18 months compared with placebo would be 33% and 50% corresponding to the 2 doses, respectively. The estimated power for the actual planned 200 mild AD subjects is at least 80% assuming a 2-sided alpha of 0.05.

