9.1.2.2 Early Discontinuation

Subjects who discontinue taking study drug prematurely for any reason will undergo an Early Discontinuation (ED) Visit within 7 days of their last dose of study drug. Follow-Up Visits will also be scheduled 4 and 12 weeks after the last dose of study drug.

Subjects who discontinue study drug prematurely will also be scheduled to return to the study site for each scheduled visit when clinical efficacy assessments are to be conducted (ie. at Visits 11, 14, 15, 16, 17, and 18, if these visits have not already been performed). At these visits, only clinical efficacy assessments (MMSE, CDR, ADAS-cog₁₄, FAQ, CBB and ISLT) will be conducted. Regularly scheduled clinical efficacy visits do not need to be attended if they fall within 8 days (visit window) after the Early Discontinuation Visit or within ± 8 days of either of the Follow-Up Visits (Visit 19 and Visit 20). Subjects who discontinue early from study drug are considered on study as long as they return for their regularly scheduled clinical efficacy visits as outlined above.

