- a. A study drug discontinuation threshold will be set based on absolute counts of CD4 (T helper cells), CD8 (cytotoxic T cells), or CD19 (B cells). The discontinuation threshold will be set at below the level of the LLN, at a level that represents a greater risk of opportunistic infection in the treated population. For CD4 (T helper cells) the discontinuation threshold is 250 cells/ μ L. For CD8 (cytotoxic T cells) and CD19 (B cells) the discontinuation thresholds are 150 cells/ μ L and 50 cells/ μ L, respectively. Any subject who has CD4 (T helper cells), CD8 (cytotoxic T cells), or CD19 (B cells) absolute counts below the discontinuation threshold as confirmed by a repeat test conducted within 1 week of the initial test will be discontinued from study drug.
- b. Subjects with CD4 (T helper cells), CD8 (cytotoxic T cells), or CD19 (B cells) absolute counts between the LLN and the discontinuation threshold will have lymphocyte subset counts performed on a weekly basis. Subjects with a >33% reduction from baseline in CD4 (T helper cells), CD8 (cytotoxic T cells), or CD19 (B cells) absolute counts will also have lymphocyte subset counts performed on a weekly basis. For these subjects, the decision as to whether the subject remains on study drug or is to be discontinued from study drug will be based upon clinical judgment and will take into account any clinical presentation in addition to the lymphocyte subset counts. These subjects may continue with treatment if there is no clinical evidence of infection. They will be discontinued from study drug if they have infections of a moderate to severe intensity (eg, subjects whose infections are not localized, or are systemically unwell, or who require systemic anti-infective drug treatment).

Table 1 Study Drug Actions for Lymphocyte Subset Absolute Counts

| Lymphocyte subset absolute counts | Action | Decision to continue or discontinue |
|--|---|---|
| CD4 (T helper cells), CD8 (cytotoxic T cells), or CD19 (B cells) absolute counts below discontinuation threshold | Retest within 1 week | If retest performed within 1 week confirms lymphocyte subset counts below the discontinuation threshold, discontinue study drug |

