Subjects who discontinue taking study drug prematurely for any reason will undergo an Early Discontinuation (ED) Visit within 7 days of their last dose of study drug. Follow-Up Visits will also be scheduled 4 and 12 weeks after the last dose of study drug. Subjects who discontinue study drug prematurely will also be scheduled to return to the study site for each scheduled visit when clinical efficacy assessments are to be conducted (ie, at Visits 11, 14, 15, 16, 17, and 18) if these visits have not already been performed. At these visits, only the clinical efficacy assessments (MMSE, CDR, ADAS-cog₁₄, FAQ, CBB and ISLT) will be conducted. Subjects who discontinue early from study drug are considered on study as long as they return for their regularly scheduled clinical efficacy visits as outlined above.

Follow-Up

All subjects, regardless of whether they complete all 18 months of treatment or discontinue study drug prematurely, will complete 2 posttreatment Follow-Up Visits; one 4 weeks after the last dose of study drug (Visit 19) and a second 12 weeks after the last dose of study drug (Visit 20). If clinically indicated, more frequent safety assessments can be conducted as part of unscheduled visits during the posttreatment Follow-Up period.

Number of Subjects

- Stage A: Approximately 250 MCI/Prodromal subjects will be screened to provide 60 randomized subjects (target of 15 subjects per treatment arm).
- Stage B: Approximately 1850 MCI/Prodromal subjects will be screened to provide up to 440 enrolled subjects. The final number of MCI/Prodromal subjects will depend upon whether the prespecified criteria for either early success or futility are met. In addition, approximately 835 subjects with mild AD will be screened to provide approximately 200 randomized mild AD subjects.

Inclusion Criteria

1. Meets the core clinical research criteria of the NIA-AA for MCI due to AD or AD dementia and is "staged" or classified as either MCI (Stage A and Stage B) or mild dementia (Stage B only) and also complies with the following:

Required at both Screening and Baseline:

- a. Subjective Memory Complaint with evidence of concern about a decline in cognition from the subject, informant, or clinician's observation
- b. Cognitive impairment of at least 1 SD from age adjusted norms in delayed recall on the ISLT
- c. FAQ ≤ 20
- d. MMSE ≥ 20

2. Amyloid positive PET image based on centralized PET scan reading

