The PD Analysis Set will be used for the summaries and analyses of PD biomarkers (CSF and plasma biomarkers, MRI endpoints). CSF A β (1-x), A β (1-42), t-tau, p-tau, and BACE1 will be assessed and data will be presented graphically. Baseline levels and changes in t-tau and p-tau will be correlated with changes in CSF A β (1-42), imaging markers, and *ApoE4* status. Summary statistics for CSF biomarkers will be assessed for evidence of a dose relationship.

Pharmacokinetic and Pharmacodynamic Analyses

The PK/PD relationship between CSF biomarker levels and exposure to E2609 in plasma and CSF will be explored graphically and any emergent relationship will be explored through population PK/PD modeling. Additionally, the relationship between CSF exposure to E2609 and the derived ADCOMS at 18 months, and the relationship between CSF exposure to E2609 and the change from baseline for 18 months in the ADAS-cog, the CDR, and the

MMSE will be explored graphically. Any emergent relationships will be explored through population PK/PD modeling.

Pharmacogenomic Analyses

Blood samples will be used to determine the *ApoE* genotype and the *NAT2* phenotype of subjects enrolled in this study. Further information is in the “[Pharmacodynamic, Pharmacogenomic, and Other Biomarker Assessments](#)” section. Details of pharmacogenomic testing may be provided and reported separately.

Safety Analyses

Evaluations of safety will be performed on the Safety Analysis Set. The incidence of AEs (including changes from baseline in physical and neurological examinations, and dermatological assessments), out-of-normal-range laboratory safety test variables, abnormal ECG findings, out-of-range vital signs, suicidality (C-SSRS), and results of the sleep questionnaire, along with the change from baseline in laboratory safety test variables, ECGs, safety MRI, and vital sign measurements will be summarized by treatment group using descriptive statistics.

Lymphocyte Subsets

Lymphocyte subsets (ie, CD4 [T helper cells], CD8 [cytotoxic T cells], CD19 [B cells], CD16/CD56 [natural killer cells] and CD14 [macrophages]) and regulatory T cells will be summarized in the same manner as other laboratory parameters. Mean lymphocyte subsets and the mean change from baseline in lymphocyte subsets will also be displayed graphically over time by dose. Serum IgG, IgM, IgA will be measured and summarized in the same manner as other laboratory parameters.

Interim Analyses

The MCI/Prodromal cohort

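### The by-dose plot of mean lymphocyte counts loses subjects who are stopped for low counts, so its later points understate a dose-related fall, most for CD8

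*Protocol*

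**What the plan says.** Section 9.7.1.8.3 and the Synopsis of Protocol Version 3.0, and the Version 2.0 Synopsis in the same words, plan two curves per subset: "Mean lymphocyte subsets and the mean change from baseline in lymphocyte subsets will also be displayed graphically over time by dose". The population is the general one: "Evaluations of safety will be performed on the Safety Analysis Set".

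Section 9.3.3 ties continued dosing to the same counts. "For CD4 (T helper cells) the discontinuation threshold is 250 cells" per µL; "For CD8 (cytotoxic T cells) and CD19 (B cells) the discontinuation thresholds are 150 cells" and 50 cells per µL respectively. A subject with "counts below the discontinuation threshold as confirmed by a repeat test conducted within 1 week of the initial test will be discontinued from study drug". Items (b) and (c) and Table 2 also stop subjects with a moderate infection whose count is between the lower limit of normal (LLN) and the stopping threshold, or has fallen by more than 33% from baseline.

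Section 9.1.2.2 then limits what is collected at the remaining scheduled visits: "At these visits, only clinical efficacy assessments" are done. Per Table 7 and its note e, a stopped subject has subsets measured at the Early Discontinuation Visit, at Visit 19 (4 weeks after the last dose), and at Visit 20 if the Visit 19 result was out of range. Item (c) of Section 9.3.3 follows infected subjects who stop for longer.

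The second primary objective (Section 8.1) is safety, with immunological and hematological parameters named.

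**The concern.** Removal depends on the plotted variable. A subject whose count falls far enough leaves the later scheduled visits, and more subjects leave in the dose that lowers counts more. The remaining mean is then too high in exactly that dose, and the gap to placebo shrinks for a reason unrelated to recovery.

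This matters because treatment goes from 14 days in the multiple-dose study to 18 months here (Section 9.2.6). Whether a lymphocyte fall persists, levels off or grows is a question that only a time course can answer. A mean-count curve that drifts back towards placebo could be read as adaptation when it is attrition.

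**Working it through.** The protocol states no figure for this display, so there is none to reproduce. The check has three parts.

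**1. How close entry is to stopping.** Fall needed from the entry limit = 1 − (stop threshold / LLN). The original LLNs and the age-adjusted ones are in Appendix 5, Table 9.

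| Marker | Stop | Original LLN | Fall | Age-adjusted LLN | Fall |
|---|---|---|---|---|---|
| CD4 | 250 | 404 | 38% | 396 | 37% |
| CD8 | 150 | 220 | 32% | 157 | 4.5% |
| CD19 | 50 | 80 | 37.5% | 74 | 32% |

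CD8 has the least room, and almost none under the age-adjusted limit. Appendix 5 belongs to a later version whose Section 9.3.3 is not shown, so pairing 157 with 150 is an assumption.

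**2. Simulating the removal rule.** Baselines were log-normal, from the combined columns of Tables 10 to 12: medians 791.5, 336.39 and 164.86. Log SD = ln(Q3/Q1)/1.349:
- CD4: ln(1039.50/633.77)/1.349 = 0.37
- CD8: ln(438/230)/1.349 = 0.48
- CD19: ln(246/104.58)/1.349 = 0.63

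Subjects below LLN on two tests were excluded. There were 15 post-dose visits, weeks 1 to 78. A subject left when a count and its repeat were both below threshold.

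Assumed, because the documents do not give them: within-subject CV 12% or 20%; mean reduction 10%, 20% or 30%; between-subject SD of the effect 15% (also 30% at the 20% reduction); and an effect either proportional to baseline or the same absolute drop for everyone. Infection stops were not simulated.

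Ratio = (drug − placebo at week 78 among those still on drug) / (drug − placebo had nobody been removed). Below 1 means understated.

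| Effect model | Removed on drug | Mean-count ratio | Mean-change ratio |
|---|---|---|---|
| Proportional, SD 15% | 2–34% | CD4 0.94–0.99; CD8 0.70–0.90; CD19 0.88–0.97 | 0.99–1.11 |
| Proportional, SD 30% | 15–28% | CD4 0.86–0.90; CD8 0.50–0.68; CD19 0.75–0.86 | 0.91–1.00 |
| Same absolute drop, SD 15% | 17–60% | 0.23–0.78 | 0.78–0.93 |
| Same absolute drop, SD 30% | 45–52% | 0.01–0.44 | 0.55–0.71 |

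One line in full, from the harsh end (same absolute drop, 20% reduction, SD 15%, CV 20%, original LLNs; 38.6% removed):
- CD8 mean count: −35.0 / −83.6 = 0.42
- CD8 mean change: −72.8 / −84.3 = 0.86
- CD4 mean count: −124.5 / −174.9 = 0.71

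The same line with the age-adjusted LLNs (43.6% removed): CD8 mean count −24.2 / −78.8 = 0.31.

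**3. Milder assumptions.** A second simulation used correlated markers (0.4), the original LLNs (a low first test was excused if the repeat was normal) and an effect building up over 12 weeks.
- Average fall 10%: 1–2% stop; mean-count difference understated by 2–6%.
- Fall 20%: 6–8% stop; understated by 10–18%.
- Fall 30%: 12–19% stop; understated by 11–30%.

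The mean-change difference was understated by 0–12%. A missing-at-random repeated-measures estimate from the same data was within about 1% of the truth.

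**Reading.** The mean-count ratio is below 1 in every scenario. The mean-change ratio is not. Removal picks out subjects with low baselines, and under a proportional effect their absolute changes are small, so losing them can enlarge the remaining mean change. It also picks out subjects with large effects, which works the other way.

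**The case against.** The strongest case on the other side has five parts.

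- **No on-drug restriction is written.** A reader might infer that the means are defined on subjects still taking drug. The text says Safety Analysis Set, and stopped subjects contribute every count up to removal. This stands: the thinning of later points follows from the visit schedule, not from an analysis rule.
- **The toxicity is reported elsewhere.** Section 9.7.1.8.3 summarises change to the last on-treatment value and the shift to the lowest value on treatment. A laboratory abnormality that leads to stopping is an adverse event (Section 9.5.1.5.1), and events leading to discontinuation are tabulated by treatment group (Section 9.7.1.8.2). The data safety monitoring board sees unblinded data about every 3 months during recruitment. This also stands: a reading that the plan conceals the effect is not supported. But none of those tables is a time course by dose.
- **Half of the planned display is not clearly biased.** Correct, as the ratios for mean change show.
- **The likely effect is small.** At 100 mg in Study 002, CD4 changed by −3.1% against +8.7% on placebo, a gap of 11.8 points, and Section 9.4.4 puts exposure at 50 mg with food below that. This points to the lower end of the range for CD4. Those data cover 14 days only, and do not settle CD8 or 18 months.
- **Figure details belong in the statistical analysis plan.** Partly so. Yet the protocol itself fixes the raw mean as the plotted quantity, and that choice is what interacts with its own stopping rule.

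**Conclusion.** The point holds for the mean-count curve. Its later values come almost entirely from subjects who stayed above the stopping thresholds, so a dose-related fall is understated, most for CD8. The direction was the same in every scenario run. The size is not derivable from the documents, because within-subject variability and the 18-month effect are not given. Under assumed effects it runs from about 2% to 30% or more, and it grows if the age-adjusted entry limits apply together with the thresholds in Section 9.3.3. The extreme ratios need the same absolute drop in every subject and should not be taken as forecasts.

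Two stronger readings should not be drawn. The mean-change curve is not shown to be understated; its bias is smaller and can take either sign. The lymphocyte effect is not hidden from the report, because the last-value, lowest-value and discontinuation tables retain the stopped subjects. What is missing is a time course by dose that is free of this selection, for a safety domain named in a primary objective.

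**What to change.** In Section 9.7.1.8.3 and the Synopsis:

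1. Keep both raw-mean plots. Add by-dose estimates over time from a likelihood-based repeated-measures model (dose, visit, dose by visit, baseline count), fitted to all on-treatment counts including the confirmatory repeats.
2. Print under each visit, by dose, the number of subjects contributing and the cumulative number stopped for low counts.
3. Do not pool off-drug counts into the curve. In the multiple-dose study the effect resolved between 6 and 21 days after the last dose (Section 7.1), so pooling would dilute it.
4. State the assumption. Missing at random is well founded for stops triggered by a recorded count. For infection-related stops, which also turn on severity and clinical judgment, it is only an assumption.

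The cost is wording and one extra model per marker. No data collection or stopping rule changes. The added figure is model-based and describes counts as if treatment had continued. If log counts are modelled, it shows geometric and not arithmetic means, and the legend should say so.

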4 LIST OF ABBREVIATIONS AND DEFINITIONS OF TERMS

| Abbreviation | Term |
|--------------------------|--|
| A β | amyloid β |
| A β (1-x) | amyloid β (1-x) (ie, the amyloid β monomer from amino acid 1 to x [eg 1-42]) |
| AChEI | Acetylcholinesterase inhibitor |
| AD | Alzheimer's disease |
| ADAS-cog | Alzheimer's Disease Assessment Scale - cognitive subscale |
| ADCOMS | Alzheimer's Disease Composite Score |
| AE | Adverse Event |
| ApoE | Apolipoprotein E |
| AUC | area under the concentration x time curve |
| AUC _{(0-24h)ss} | area under the concentration x time curve at steady state from time zero to 24 hours |
| BACE1 | Beta-amyloid converting enzyme 1 |
| BP | blood pressure |
| bpm | beats per minute |
| CBB | CogState Brief Battery |
| CBP | childbearing potential |
| CDR | Clinical Dementia Rating |
| CES2 | carboxyesterase-2 |
| CFR | Code of Federal Regulations |
| C _{max,ss} | maximum plasma concentration at steady state |
| CMV | cytomegalovirus |
| CNS | central nervous system |
| CRA | clinical research associate |
| CRF | case report form |
| CRO | contract research organization |
| CSF | cerebrospinal fluid |
| C _{ss,av} | average steady-state concentration |
| C-SSRS | Columbia Suicide Severity Rating Scale |
| CTA | Clinical Trial Agreement |
| CYP | cytochrome P450 |
| d _{Max} | Maximum effective dose |
| DSMB | data safety monitoring board |
| ECG | electrocardiogram |
| eCRF | electronic case report form |

| Abbreviation | Term |
|---------------------|---|
| ED | early discontinuation |
| ED ₉₀ | lowest effective dose that achieves 90% of the greatest treatment effect |
| ELISA | enzyme-linked immunosorbent assay |
| FAQ | Functional Assessment Questionnaire (also known as the Functional Activities Questionnaire) |
| FAS | Full Analysis Set |
| FDA | Food and Drug Administration |
| FLAIR | fluid-attenuated inversion recovery |
| GCP | Good Clinical Practice |
| GDS | Geriatric Depression Scale |
| HBsAg | hepatitis B surface antigen |
| hCG | human chorionic gonadotropin |
| HCVAb | hepatitis C virus antibody |
| HSV | herpes simplex virus |
| ICF | informed consent form |
| ICH | International Conference on Harmonisation of Technical Requirements for Registration of Pharmaceuticals for Human Use |
| ID | identifier |
| IEC | Independent Ethics Committee |
| Ig | immunoglobulin (eg, IgA, IgG, IgM) |
| INR | International Normalized Ratio |
| IRB | Institutional Review Board |
| ISLT | International Shopping List Task |
| IxRS | interactive voice and web response system |
| LLN | lower limit of normal |
| LNH | low/normal/high |
| LP | lumbar puncture |
| MAD | multiple ascending dose |
| MCI | mild cognitive impairment |
| MCI/Prodromal | Mild Cognitive Impairment due to Alzheimer's Disease/ Prodromal Alzheimer's Disease |
| MedDRA | Medical Dictionary for Regulatory Activities |
| mild AD | mild dementia due to Alzheimer's Disease |
| miRNA | micro-ribonucleic acid |
| MMRM | mixed-effects model with repeated measures |
| MMSE | Mini Mental State Examination |
| MRI | magnetic resonance imaging |

| Abbreviation | Term |
|---------------------|--|
| NAT2 | N-acetyltransferase 2 |
| NIA-AA | National Institute on Aging-Alzheimer's Association |
| OF | O'Brien-Fleming |
| PBMC | peripheral blood mononuclear cell |
| PD | Pharmacodynamic(s) |
| PET | positron emission tomography |
| PGx | pharmacogenomic(s) |
| PK | pharmacokinetic(s) |
| PP | per protocol |
| PRN | Pro re nata |
| PT | prothrombin time |
| PTT | partial thromboplastin time |
| p-tau | phosphorylated-tau |
| QD | once daily |
| QTc | corrected QT interval |
| QTcF | QTc interval calculated using Fridericia's formula |
| R | randomization |
| SAD | single ascending dose |
| SAE | serious adverse event |
| SOC | system organ class |
| SUSAR | suspected unexpected serious adverse reaction |
| SUVR | standardized uptake value ratio |
| TB | tuberculosis |
| TEAE | treatment-emergent adverse event |
| TEMAV | treatment-emergent markedly abnormal laboratory values |
| t-tau | total tau |
| ULN | upper limit of normal |
| UNS | unscheduled |
| vMRI | volumetric magnetic resonance imaging |
| WHO DD | World Health Organization Drug Dictionary |
| β -hCG | beta-human chorionic gonadotropin |

Study References: On first use, the full study code will be used (eg, E2609-G000-202) with a shortened form in brackets (Study 202); thereafter, the shortened form is used.

